Clinical Investigation Plan

Study Title: Comparison of clinical performance and subjective preference out of three cosmetic contact lenses (limbal ring-enhancing lenses, LRE lenses)

SPONSOR: CooperVision Korea, Inc.

CLINICAL SITE: School of Optometry & Vision Science, Catholic University of

Daegu, Korea (Rep)

PROTOCOL DATE: October 21, 2016

PROPOSED START DATE: Dec, 2016

STUDY TITLE:

Comparison of clinical performance and subjective preference out of three cosmetic contact lenses (limbal ring-enhancing lenses, LRE lenses)

· · · ·

SPONSOR COMPANY: COOPERVISION KOREA, INC.

DOCUMENT TYPE: PROTOCOL

PRINCIPAL INVESTIGATOR:

DOCUMENT PREPARED BY:

DOCUMENT REVEIWED AND APPROVED BY:

Study summary

This bilateral subject-masked, randomized, crossover dispensing study will investigate the clinical performance **Control of the Hydron 1-day cosmetic contact lens** (Hydron Inc.), when compared to the 1-day Acuve Define (Johnson & Johnson Vision Care Inc.) and Claren 1-day Iris (Interrozzo Inc). Sixty subjects will be enrolled into this three-week study, where they will wear each lens type for one week. The order of lens wear will be randomized so that the effects related to order are minimized. The outcome measures will divided into subjective and objective measure. Primary subjective measure

Table 1: Study summary

Section 1. Overview

1.1 Background

Contact lenses markets has been steadily increased. One of driving factors for growing market is a cosmetic contact lenses which is designed to change the appearance of their eye in addition to correction of refractive error. With its popularity, there are many cosmetic contact lenses available in market and personnel preference are all different. Therefore, this study aims to evaluate the performance of a new daily disposable limbal ring lens, Hydron-1day (Hydron Inc), compared to the existing daily disposable limbal ring lens, 1.Day ACUVUE[®] Define[™] (Johnson & Johnson Vision Care Inc) and Claren 1-day Iris (Interrozzo Inc). Limbal ring lenses are cosmetic lenses which enlarge and define the wearer's iris and are particularly popular in East Asian countries.

1.2 Personnel

1.3 Study Objectives

The purpose of this study is to evaluate the clinical performance out out
of three LRE lens types; 1-day Acuve Define, Claren 1-day Iris and Hydron 1-day cosmetic
contact lenses. Clinical performance measures will include comfort,

1.4 Study Design

This will be a subject-masked if possible, bilateral, randomized, crossover dispensing study to compare clinical performance and subjective preference out of three lens types. Sixty subjects will be assigned into three groups and each group will wear the test and control lenses as matched pairs for one week each in random order. Lenses will be worn on a daily wear, daily disposable schedule.

Figure 1. Grouping and lens randomization order

1.5 Statistical considerations

The prinicpal null hypothesis is that the comfort for the three lens types are equal. Prior to statistical analysis, normality of data will be assessed. Ordinal measure such as lens fit, biomicroscopy

Deviations from this

statistical plan will be discussed in the final report.

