1.5.1 Power analysis

Study sample size was estimated a priori for the principal outcome measure, the subject's preference with respect to attractiveness. We are testing the null hypothesis that there is no difference in the subject's preference with respect to attractiveness between the three lens types. The sample size was estimated using G* Power, to detect a small effect size of 0.20, α =0.05 for one group, three repetitions and an assumed correlation of 0.5 amongst the repeated measures with a power of 0.90. The total sample size was estimated at 55. To allow for discontinuations, 60 participants will be recruited.

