3.2.2 One-week follow-up visit

Subjects should attend wearing the study lenses which should have been in situ for at least

two hours. Subjects who attend without lenses in situ for at least two hours will usually be rescheduled. The following procedures will be performed (any ocular measurement procedures outlined below will be carried out on each eye):

1. Lens wearing times since the previous visit will be recorded.

2. Lens wearing time on study visit day.

3. Monocular logMAR visual acuity (high contrast) with the study lens.

4. The subject will be asked to score the following qualities using a visual analog scale for:

Comfort after insertion

Comfort before removal

Orverall comfort	
Overall comfort	

7. The lenses will then be removed and discarded.

8. The investigator will then conduct a complete biomicroscopic examination of the clinical signs

9. The second pair of lenses will be applied

10. Visual acuity & lens fit will be assessed with second pair of lenses worn

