3.2.3 Two and Three-week visit

Subjects should attend wearing the study lenses which should have been in situ for at least two hours. Subjects who attend without lenses in situ for at least two hours will usually be rescheduled. The following procedures will be performed (any ocular measurement procedures outlined below will be carried out on each eye):

1. The same procedures as the 1-week visit (3.2.2) sections 1-10 will be carried out.

2. Additionally, subjects will be asked to rank the lens in order of preference.

3. At the final visit (or when the subject is discontinued at an earlier visit) the subject will sign a study exit statement acknowledging that the work is complete, although they may have been asked by the investigator to attend a post-study follow-up visit, and that they should continue to use their lenses and solutions as advised, and seek aftercare for their contact lenses. A copy of this signed form will be issued to the subject.

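### Sections 1.5 and 1.5.1 name different principal hypotheses (comfort versus attractiveness preference), and the sample size is justified only for attractiveness

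*Combined protocol and SAP*

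**What the plan says.** Section 1.5 (Statistical considerations) puts comfort first: "The prinicpal null hypothesis is that the comfort for the three lens types are equal".

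Section 1.5.1 (Power analysis) names another outcome: "Study sample size was estimated a priori for the principal outcome measure, the subject's preference with respect to attractiveness". It follows this with its own hypothesis: "We are testing the null hypothesis that there is no difference in the subject's preference with respect to attractiveness between the three lens types". The calculation was done in G*Power "to detect a small effect size of 0.20", with α = 0.05, one group, three repetitions, an assumed correlation of 0.5 among the repeated measures and power 0.90. It gives 55 subjects, raised to 60 to allow for discontinuations.

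The two outcomes are different measurements. Section 3.2.2 collects comfort on visual analog scales at three points: after insertion, overall, and "Comfort before removal". For preference, the readable text of section 3.2.3 provides a ranking: "subjects will be asked to rank the lens in order of preference".

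**The concern.** A trial with one 0.05 test and one sample size needs one principal hypothesis. Here two adjacent sections each call a different outcome principal. A report that treated comfort as decisive could cite 1.5, one that treated attractiveness as decisive could cite 1.5.1, and neither would count as a deviation from the plan.

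Two things are at stake.

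- **Power.** If comfort is taken as principal and shows no difference, the result could be presented as a null finding with 90% power, although the 90% was derived for another outcome.
- **Error rate.** If the choice is made after the data are seen, or if either outcome may be claimed at 0.05, the chance of a false claim exceeds 5%. If one outcome is fixed beforehand, it does not.

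**Working it through.** **1. Could missing text explain the conflict?** Parts of the study summary and of sections 1.3, 1.5 and 3.2.2 are missing from the public copy. The two conflicting statements are whole, however. Missing text might add an ordering or co-primary rule, but it could not make these two statements name the same principal outcome. No claim is made here that such a rule is absent.

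**2. Reproducing the plan's sample size.** Inputs from 1.5.1: effect size f = 0.20, m = 3 repetitions, one group, ρ = 0.5, α = 0.05, power 0.90. The plan does not name the effect-size index. It is read here as Cohen's f for a repeated-measures F test, with sphericity assumed.

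Formula: λ = f² × N × m / (1 − ρ), with df₁ = m − 1 = 2 and df₂ = (N − 1)(m − 1) = 2(N − 1). Power is the noncentral F probability beyond the 5% critical value.

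| N | λ | df₂ | Power |
|---|---|---|---|
| 54 | 0.04 × 54 × 3 / 0.5 = 12.96 | 106 | 0.899 |
| 55 | 0.04 × 55 × 3 / 0.5 = 13.20 | 108 | 0.904 |
| 60 | 0.04 × 60 × 3 / 0.5 = 14.40 | 118 | 0.929 |

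The smallest N reaching 0.90 is 55, exactly as stated. The arithmetic is not at fault.

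**3. What this implies for comfort.** The readable text gives no effect size or correlation for comfort, so the values below are assumptions chosen to show the range. All are at N = 60 and α = 0.05.

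| f | ρ | λ | Power |
|---|---|---|---|
| 0.20 | 0.5 | 14.40 | 0.929 |
| 0.20 | 0.3 | 0.04 × 180 / 0.7 = 10.29 | 0.817 |
| 0.20 | 0.7 | 0.04 × 180 / 0.3 = 24.00 | 0.994 |
| 0.15 | 0.5 | 0.0225 × 180 / 0.5 = 8.10 | 0.712 |
| 0.25 | 0.5 | 0.0625 × 180 / 0.5 = 22.50 | 0.991 |

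At f = 0.20, the N needed for 0.90 power is 76 at ρ = 0.3, 55 at ρ = 0.5 and 34 at ρ = 0.7.

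**4. Error rate if either outcome may be claimed at 0.05.** With independent outcomes it is 1 − 0.95² = 0.0975. For correlated outcomes, two such F tests were simulated at N = 60 (200,000 trials). The rates were about 0.091, 0.085 and 0.072 at between-outcome correlations of 0.5, 0.7 and 0.9.

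**5. Side check on the test.** The 0.90 belongs to an F test on scores. If attractiveness were recorded only as ranks and analysed by the Friedman test, simulation with normal data and the same inputs gives power of about 0.78 at N = 55 and 0.82 at N = 60. This is conditional, because an attractiveness scale may stand in the missing part of 3.2.2, where the numbering jumps from item 4 to item 7.

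**The case against.** The strongest reply concedes the contradiction and disputes its consequences.

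- **The inputs are generic.** An effect of 0.20 and a correlation of 0.5 are standardised assumptions with no attractiveness data shown behind them, so 55 carries over to comfort if the same values are assumed. This is correct, and it is why underpowering for comfort is not claimed. The ranges in the working are ordinary sensitivity and do not measure harm already done. Carrying the figure over would still be a step the plan does not take, and it would not settle which outcome is principal.
- **The error rates depend on a condition that cannot be established.** A rule may be in the missing text, and 9.75% requires independence although the same subjects rate the same lenses. Both points stand. The figures apply only if either claim is allowed, and the correlated values are the more realistic ones.
- **The Friedman figures concern a separate matter and rest partly on missing text.** This also stands. The finding does not need them.
- **Aligning to attractiveness picks a winner.** Attractiveness is the only outcome the readable text sizes, so this is the shortest correction. The sponsor may still choose comfort, provided the sizing follows.

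**Conclusion.** The concern holds and must be fixed before the data are analysed. The plan names two different outcomes as principal, and this does not come from missing text. The sample size of 55 is arithmetically right for the outcome in 1.5.1, reading the effect as Cohen's f with sphericity. For the outcome in 1.5, the readable text gives no power justification, and the assumed scenarios at 60 subjects span 0.712 to 0.994. The false-positive rate is 5% if one outcome is fixed beforehand. If either may be claimed at 0.05, it is about 7.2% to 9.1% at between-outcome correlations from 0.9 down to 0.5, and 9.75% under independence. Confidence is high for the contradiction itself; the numerical consequences are conditional as described.

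**What to change.** **Preferred change.** Correct 1.5 so that its principal hypothesis is the outcome sized in 1.5.1, preference for attractiveness. State that it is analysed by the repeated-measures F test used for sizing, or restate the power for the test that will be used. Make overall comfort a secondary outcome, or test it second in fixed order at 0.05 only if the attractiveness test rejects.

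**Alternative.** If the sponsor intends comfort as principal, name one comfort scale in 1.5 and rewrite 1.5.1 with an effect size and correlation justified for that scale.

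**Cost.** The preferred change takes one or two sentences and needs no extra subjects or data, provided attractiveness is analysed as sized. If it is analysed as ranks, the power must be restated and 60 subjects may fall short of 0.90. Either way, a claim on the other outcome becomes secondary or conditional. Under the alternative, N could move in either direction: for example 76 at f = 0.20 and ρ = 0.3, or 34 at ρ = 0.7, before any allowance for discontinuations.

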1.5.1 Power analysis

Study sample size was estimated a priori for the principal outcome measure, the subject's preference with respect to attractiveness. We are testing the null hypothesis that there is no difference in the subject's preference with respect to attractiveness between the three lens types. The sample size was estimated using G* Power, to detect a small effect size of 0.20, α =0.05 for one group, three repetitions and an assumed correlation of 0.5 amongst the repeated measures with a power of 0.90. The total sample size was estimated at 55. To allow for discontinuations, 60 participants will be recruited.

1.6 Risk analysis

There are no expected risks in this study other than wearing contact lenses. Also all subjects enrolled in this study will be existing contact lens wearers, therefore all subjects are very familiar with handling contact lenses.

1.7 Ethics Review and statement of compliance

Ethical approval will be sought from the Institutional Review Board Catholic University of Daegu (hereafter referred to as CU IRB, [contact], e-mail address: [contact]). The work where practical will be conducted in accordance with the ICH Good Clinical Practice Guidelines and the international standard BS EN ISO 14155:2011 'Clinical investigation of medical devices for human subjects'. This study will be registered with clinicaltrials.gov in accordance with section 801 of the Food and Drug Administration (FDA) Act which mandates the registration of certain clinical trials of drugs and medical devices.

Section 2. Resources

2.1 Subject selection

Sixty subjects who are currently existing contact lenses wearers will be enrolled. Out of 60 subjects, twenty subjects will be recruited from the current wearers of 1.Day ACUVUE[®] DefineTM (Johnson & Johnson Vision Care Inc) and another twenty subjects will be current wearers of Claren 1-day Iris (Interrozzo Inc). Rest twenty subjects will be no previous wearer of any study lenses. All subjects will go through the screening procedure to ensure they satisfy the inclusion criteria. At the screening visit, a detailed Participant Information Sheet explaining the nature of the study will be provided to potential subjects along with a Participant Instruction Sheet, which includes study-specific instructions as well as general lens wear precautions. Once subject agrees to participate, then will be asked to sign a written consent form to confirm their agreement to participate the study.

2.1.1 Subject withdrawal and replacement

Subject's participation in this study is voluntary. Subjects have the right to withdraw from participation at any time during the study without comment or penalty. Withdrawal from the study will not impact upon current or future relationship with the School of Optometry & Vision Science, Catholic University of Daegu. Subjects who have agreed to enroll the study, but have not completed the dispensing visit will be replaced.

2.1.2 Subject recruitment

Subjects will be recruited by one or more of following means:

- 1. Posting study details on the notice board of the optometry clinic in the Catholic University of Daegu.
- 2. Advertising through the optometry clinic around the Catholic University of Daegu

2.1.3 Inclusion criteria

Subjects will be only eligible for the study if they meeting the following inclusion criteria:

- 1. Age of 18 years and above and has full legal capacity as a volunteer
- 2. Understand the rights as a research subject and willing and able sign a statement of informed consent.
- 2. Existing soft contact lens wearers or previous experience of contact lens wear
- 3. Being able to wear the study lenses for at least eight hours a day
- 4. At least 6/9 visual acuity in each eye with the study lenses
- 5. Astigmatism less than 1.50 D in both eyes
- 5. Agreed to follow the protocol and not to participate in other clinical research for the duration of this study.

2.1.4 Exclusion criteria

Subjects will not be eligible to take part in the study if they:

- 1. Have an ocular disorder which would normally contraindicate contact lens wear.
- 2. Have a systemic disorder or any infectious diseases which would normally contraindicate contact lens wear.
- 3. Have previously had any ocular surgery such as corneal refractive surgery
- 4. Have less than 6/9 visual acuity in each eye with the study lenses
- 5. Are currently using any topical medication such as eye drops or ointment.

6. Have any corneal distortion resulting from previous rigid lens wear or have keratoconus.

- 7. Are currently pregnant or lactating.
- 8. No previous contact lens wear

2.2 Subject discontinuation

All subjects have the right to discontinue the study at any time. Also subjects will be discontinued if a serious adverse event occurs or non-compliance of study protocol.

2.3 Safety parameters, adverse events and concurrent illnesses

Any adverse events either the study lens related or non-study lens related will be described as anticipated condition. These adverse event are classified as 'serious', 'significant', or 'non-significant' by clinical assessment. Any adverse events occurring during the study period must be recorded. The clinical course of each event should be followed until resolution.

2.3.1 Investigator obligations

All potential Serious and Unanticipated Adverse Device Effects that are related or possibly related to subject participation in the investigation will be reported to the Principal Investigator and to the designated medical monitor of the sponsor within 24 hours of the investigator becoming aware of the event. The Principal Investigator will report the event to the EC/IRB as soon as possible (by fax, mail/delivery, phone, or email), but within 10 business days of becoming aware of the problem. All fatal or life threatening events will be reported immediately to the IRB. Significant and Non-Significant Adverse Events will be reported to the sponsor and the study coordinator as soon as possible, but no later than 5 working days after the occurrence. Sponsor medical monitor contact details are:

2.4 Study termination

If study needs to terminate earlier than planned due to any reason, the Industrial Contact Person will notify the Principal Investigator who will end the study with the cooperation of other staff members. CU IRB will be informed.

2.5 Protocol deviations

If there is any protocol deviation, these will be recorded and reported to the Industrial Contact Person. CU IRB will be informed as necessary.

2.5.1 Protocol amendments

Any amendments will be agreed between the Industrial Contact Person and the Principal Investigator with the cooperation of other staff members. Amendments will be recorded, identified and distributed. Approval from CU IRB will be obtained as necessary.

2.6 Study resources

Study products will be stored according to the manufacturer's product instructions.

2.6.1 Lenses

	1-day Acuve Define	Claren 1-day Iris	Hydron 1-day
Manufacturer	Johnson&Johnson	Interozzo	Coopervision
Replacement	1-day	1-day	1-day
Material	Etafilcon A	Methafilcon A	Methafilcon A
Water Content (%)	59%	55%	55%
Base curve (mm)	8.5mm	8.6mm	?
Lens diameter (mm)	14.2	14.2	?
Power (D)	0.00, -0.50 ~ -	0.00, -0.50 ~ -	?
	6.00(0.25steps)	6.00(0.25steps)	
	-6.50 ~ -9.00(0.50steps)	-6.50 ~ -10.00(0.50steps)	
Wearing schedule	Daily disposable	Daily disposable	Daily disposable

Details of the study lenses are provided in Table 2.

 Table 2: Study contact lens parameters

2.6.1.1 Use of lenses

The lenses in this study will be all daily disposable lenses, therefore it will be only worn on a daily wear with a minimum of eight hours per day, five days a week.

2.6.2 Care regimens

No care regimen will be required, as the lenses are to be worn on a daily disposable basis

2.6.3 Inventory control

All lenses will be supplied by CooperVision Inc. All worn lenses will be discarded.

2.6.4 Clinical equipment

Clinical equipment such as **example and and** is regularly maintained and calibrated as required. Standard operating procedures and international standards are used where appropriate.

2.7 Study control

The study design is controlled crossover comparison design. The order to wear the lenses will be pseudo-randomized to minimize the impact of order. The lenses will be masked if possible by covering name of contact lens brand.

2.8 Documentation

Documents related to this work that require archiving will be kept by the School of Optometry & Vision Science for a period of 5 years after completion of the final report, before being destroyed.

2.9 Data collection and analysis

Data collected in this work will be recorded on a spreadsheet format. This spreadsheet will be exported into a statistical package for analysis.

2.10 Study completion

The study is complete when all subjects have signed the exit statement.

2.11 fidentiality

All matters and responses are anonymous and will be treated confidentially. The name of individual persons are not required in any of the responses and subjects will only be referred by their unique identity number in the study report. No individual will be identified in any presentation or publication.

2.12 Study monitoring

In order to provide quality control and quality assurance as part of this work, the study monitor will:

- 1. Liaise closely with the Principal Investigator.
- 2. Monitor and ensure the safety of the subjects.
- 3. Ensure that the investigation is being conducted according to the protocol.
- 4. Monitor and review (or oversee review of) the study records to ensure accuracy.
- 5. Document their observations in the monitoring report for the study and make them available to relevant authorised parties (e.g. CU IRB).

Section 3. Subject management

3.1 Visit scheduling

Subjects will be required to attend for up to four visits –an initial dispensing visit, and three follow-up visits. Acceptable date ranges are shown in Table 3.

Visit	Target day to visit	Allowable range
Initial dispensing	NA	NA
One week	7 days from dispensing visit.	5-10 days from dispensing visit
Two week	7 days from dispensing visit.	5-10 days from dispensing visit
Three week	7 days from dispensing visit.	5-10 days from dispensing visit

3.1.1 Unscheduled visits

If any subjects experience any discomfort or problem with the study lenses, they will be asked to return to the clinic to be examined. This visit will be classified as 'unscheduled'. All necessary documentation such as the reason for the visit, clinical findings and action taken will be recorded on the clinical study database.

